### 9.2 Determination of Sample Size

There is no formal sample size calculation. Approximately 300 *de novo* subjects as well as approximately 300 subjects who completed the RB-US-13-0001 efficacy study will be enrolled into this study to ensure at least 100 subjects reach 1 year of treatment with RBP-6000.

### 9.3 Analysis Populations

The following populations will be used for data analyses:

#### 9.3.1 Safety Population

The Safety Population comprises all subjects who received at least 1 dose of RBP-6000 during the open-label treatment phase of the study. This population will be used for all safety analyses.

#### 9.3.2 Clinical Outcome Assessment and PK Populations

The Clinical Outcome Assessment population will include subjects who were dosed with RBP-6000 and have at least 1 post-dose Clinical Outcome Assessment value.

The PK Population will include any subject who receives a dose of RBP-6000 or at least 1 dose of SUBOXONE sublingual film and has at least 1 sample collected post-dose.

## 9.4 Demographics and Baseline Characteristics

Demographic and baseline characteristics (gender, race, age, weight, height) will be summarized by treatment group using descriptive statistics. Qualitative variables (gender, race) will be summarized using frequencies while quantitative variables (age, weight, height) will be summarized using mean, SD, median, minimum, and maximum.

## 9.5 Primary Analysis

### 9.5.1 Safety Endpoints

Safety variables will include AEs, local injection site tolerability (e.g., injection site grading); injection site pain using a subject-reported VAS; suicidality using the eC-SSRS, concomitant medications; changes in clinical laboratory results (hematology, chemistry and urinalysis); vital sign measurements; 12-lead ECGs, physical examination results; body weight, height, BMI, and abdominal fat measurement (waist-to-hip ratio). Safety variables will be analyzed using the safety population.

Baseline is defined as the last non-missing value prior to SC injection on Day 1. No imputation of missing values will be performed.

#### 9.5.1.1 Adverse Events

All AEs will be coded using the most up-to-date version of the Medical Dictionary for Regulatory Activities (MedDRA) and reported to the FDA. AEs that began more than 30 days after the last study subject assessment day will not be included in the safety analysis. Only TEAEs occurring post administration of RBP-6000 will be included in the safety analysis (See [Section 6.10.10](#)).

The incidence of AEs (number and percent of subjects reporting the AE at least once during the study) will be summarized for all AEs, by the relationship to study drug and by severity.

#### 9.5.1.2 Laboratory Data

At each visit where clinical laboratory assessments are conducted, summary statistics for the absolute laboratory value and the changes from baseline will be presented.

#### 9.5.1.3 Vital Signs

Vital signs measurements will be assessed for clinical relevance and be performed as deemed medically necessary by research personnel. Vital signs will be taken after the subject has completed a minimum 3-minute rest in the supine position. Systolic and diastolic BP measurements will be assessed while supine throughout the trial.

#### 9.5.1.4 Other Variables Related to Safety

Results from 12-lead ECGs will be categorized as normal, abnormal clinically significant, or abnormal not clinically significant and will be summarized by time point using frequency counts

and percentages. ECG interval measurements as well as change from baseline will also be summarized by time point using descriptive statistics (mean, median, SD, minimum, maximum). Additional analysis of ECG parameters will be outlined in the SAP.

Medical history will be coded using MedDRA and summarized by treatment group as described for AEs (Section 9.5.1.1). Body weight, height, BMI, and abdominal fat measurement (waist-to-hip ratio) will be summarized using descriptive statistics (mean, median, SD, minimum, maximum), including change from baseline.

Total eC-SSRS scores will be summarized using descriptive statistics (mean, median, SD, minimum, maximum), including change from baseline. Subjects' self-reported illicit drug use from the TLFB will be summarized as descriptive statistics.

Prior and concomitant medications will be coded using the most recent version of the World Health Organization (WHO) Drug dictionary. Incidence (number and percent of subjects reporting the medication at least once during the study) will be summarized for all concomitant medications.

Local injection site tolerability as assessed by the Injection Site Grading scale will be summarized by category and severity using frequency counts and percentages similar to summaries for AEs (Section 9.5.1.1). Injection Site Pain VAS scores will be summarized by dose, injection, and time point after injection. The burning/stinging categorical variable (Yes/No) will be summarized by percent of responses in each treatment.

## 9.6 Secondary Analysis

### 9.6.1 Clinical Outcomes Assessments

COWS, SOWS and Opioid Craving VAS total scores will be summarized using descriptive statistics (mean, median, SD, minimum, maximum), including change from baseline. Subjects' self-reported illicit drug use from the TLFB will be summarized using descriptive statistics.

The cumulative distribution function (CDF) of the percentage of urine samples negative for opioids and that of the percentage of self-reports from the TLFB negative for illicit opioid use will be calculated. Other outcome efficacy measures will be estimated using descriptive statistics.

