### **Clinical Outcomes Assessments:**

COWS, SOWS and Opioid Craving VAS total scores will be summarized using descriptive statistics (mean, median, SD, minimum, maximum), including change from baseline. Subjects' self-reported illicit drug use from the TLFB will be summarized as descriptive statistics.

The cumulative distribution function (CDF) of the percentage of urine samples negative for opioids, the CDF of the percentage of self-reports from the TLFB negative for illicit opioid use, and other outcome measures will be calculated.

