4.2 Secondary Variables

The following secondary variables will be evaluated to analyze clinical outcomes:

- COWS total score.
- SOWS total score.
- Opioid Craving VAS total score.
- Self-reported illicit drug use.
- Percentage of negative urine drug screen samples.

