The suicidal ideation intensity rating is the sum of the five intensity item scores to create a total score (range 0 to 25). The five intensity items include frequency, duration, controllability, deterrents, and reason for ideation. Each item is scored from 0 to 5 with 5 representing the most severe intensity.

Suicidal Behavior Scoring

The suicidal ideation score ranges from 0 to 5 and depends on the answers to the suicidal behavior portion of the eC-SSRS. The score is the maximum suicidal ideation category (in the following order: 1 = preparatory acts or behavior, 2 = aborted attempt, 3 = interrupted attempt, 4 = actual attempt, and 5 if the subject has an AE with a preferred term of completed suicide. If all answers to these questions are "No" and the subject does not have an AE with a preferred term of completed suicide then the suicidal behavior score is 0.

Treatment Duration (weeks)

Treatment duration will be defined as $(\text{treatment stop date} - \text{treatment start date} + 1)/7$ where treatment stop date is defined as date of last RBP-6000 injection + 28 days.

Sponsor: Indivior Inc.
 Protocol no: RB-US-13-0003

Percentage of Urine Drug Screen and Self-Report Results

Subjects' self-reported illicit drug use from the TLFB and results from the UDS will be combined into a single endpoint in the following manner:

- If both the TLFB and the UDS have a negative result at a particular visit, then the visit will be considered to have a negative result at that visit.
- If either the TLFB or UDS, or both, have a non-negative result at a particular visit, then the visit will be considered to have a non-negative result at that visit.
- To be conservative, missing UDS or TLFB data will be imputed as non-negative.

Urine Drug Screen Result for Opioids	Self-Report of Illicit Opioid Use Result	Overall Result
Nonnegative	Nonnegative	Nonnegative
Nonnegative	Negative	Nonnegative
Negative	Nonnegative	Nonnegative
Negative	Negative	Negative

Treatment Success

A subject is defined as a treatment success if $\geq 80\%$ urine samples negative combined with self-reports negative.

Visit Window for Remapping of Early Termination visit

Duration will be derived in days as (ET visit date – treatment start date) + 1.

Sponsor: Indivior Inc.
 Protocol no: RB-US-13-0003

Visit window for safety and efficacy assessments.

Study Visit	Lower Window for Analysis Day (ADY)	Upper Window for ADY
Week 1 Day 1	1	1
Week 1 Day 2	2	5
Week 2 Day 8	6	12
Week 3 Day 15	13	19

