9.5.1 Self-reported and Urine Samples Illicit Drug Use

Urine Drug Screen Result

A subject will be deemed to have a 'non-negative' result for opioids when his/her urine drug screen result is greater than the upper limit of normal for any of the opioid drugs tested ([Section 9.6.2.4](#)).

Opioid Drug Classification (UDS)

Drug	Opioid?
Amphetamine	No
Barbiturates	No
Benzodiazepine	No
Benzoyllecgonine	No
Buprenorphine ¹	No
Cannabinoids	No
Codeine	Yes
Hydrocodone	Yes
Hydromorphone	Yes
Methadone	Yes
Morphine	Yes
Opiate	Yes
Oxycodone	Yes
Oxymorphone	Yes
Phencyclidine	No

¹ Buprenorphine urine testing for de novo subjects was only included during the screening period; and urine testing for buprenorphine during the screening period was subsequently removed from the protocol per protocol amendment #1. The only subjects who tested positive during screening (when RBP-6000 was not being administered) were de novo subjects. Roll-over subjects were not tested for buprenorphine during screening. Neither de novo nor roll-over subjects were tested for buprenorphine at baseline or post-RBP-6000 administration.

Opioid Drug Classification (TLFB)

Drug	Opioid?
Amphetamine/Methadone ¹	Yes
Barbiturates	No
Benzodiazepine	No
Buprenorphine	Yes
Cocaine	No
Ethanol	No
Methadone	Yes
Opioids	Yes
PCP	No

¹ The TLFB interview called for an assessment of the use of amphetamine/methamphetamine. However, the ePRO tablet was programmed to ask for the use of amphetamine/methadone. As a result, the primary analysis for the TLFB question of amphetamine/methadone will be assumed to be non-negative. A sensitivity analysis will be performed where the answer to the TLFB question of amphetamine/methadone of 'Use' will be assumed to be negative.

Subjects' self-reported illicit drug use from the TLFB and opioid detection from the UDS will be summarized together by showing the number and percentage of subjects who have ≥ 0 , $\geq 10\%$, $\geq 20\%$, $\geq 30\%$, $\geq 40\%$, $\geq 50\%$, $\geq 60\%$, $\geq 70\%$, $\geq 80\%$, $\geq 90\%$, $\geq 100\%$ negative result and a continuous summary of the percent negative. The cumulative distribution function (CDF) of the percentage abstinence (negative self-reports from the TLFB combined with negative UDS for opioid use) will be presented in a graph. The graph will present the proportion of subjects who remained at least a given percentage abstinent from opioid drug

Sponsor: Indivior Inc.
Protocol no: RB-US-13-0003

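### The SAP replaces the protocol's separate urine and self-report CDFs with one combined CDF, does not list the change, and gives neither source its own percent-negative analysis

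*Protocol*

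**What the plan says.** Protocol 9.6.1 plans CDFs for two measures, "the percentage of urine samples negative for opioids and that of the percentage of self-reports from the TLFB negative for illicit opioid use", and also descriptive statistics for self-reported illicit drug use. The protocol synopsis names the same two curves as separate items: "The cumulative distribution function (CDF) of the percentage of urine samples negative for opioids, the CDF of the percentage of self-reports from the TLFB" and so on.

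SAP 5.0 (percentage of UDS and self-report results) says the two sources "will be combined into a single endpoint in the following manner". A visit is negative only if both are negative, and "missing UDS or TLFB data will be imputed as non-negative". SAP 9.5.1 then plans a single curve: "The cumulative distribution function (CDF) of the percentage abstinence (negative self-reports from the TLFB combined with negative UDS for opioid use) will be presented". The percent-negative categories, the time to first non-negative result, and the SAP 5.0 definitions of abstinence and treatment success (at least 80% negative) all use both sources.

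SAP 4.2 still lists "Percentage of negative urine drug screen samples" as a secondary variable, with self-reported illicit drug use as another. SAP 1.1 lists six changes from the protocol. None concerns these CDFs or the combined endpoint.

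One TLFB item was faulty. SAP 9.5.1 records that "the ePRO tablet was programmed to ask for the use of amphetamine/methadone" when amphetamine/methamphetamine was intended. The primary analysis counts the item as opioid use. A sensitivity analysis counts a positive answer on it as negative.

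**The concern.** An analysis that the protocol describes, for variables that the SAP still names, has no counterpart in the SAP's methods. Protocol 9.1 says that deviations from the described analyses will be included in the SAP, and SAP 1.1 is where the SAP collects them, including the dropped repeated-measures model for the clinical outcomes. A reader comparing the two documents is not told that this analysis changed.

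What is lost is the ability to attribute a result. If the combined percentage is low, the reader cannot tell whether the cause is positive urines, self-reported use, missing interviews or the faulty item. A per-subject urine percentage does not depend on any of the TLFB causes.

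**Working it through.** The documents state no figure on this point, so there is nothing to reproduce. The check is a comparison of the planned outputs, followed by illustrative arithmetic.

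**1. What each source gets on its own**

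- Per-subject percentage of opioid-negative urines, with CDF: planned in protocol 9.6.1, absent from the SAP text.
- Per-subject percentage of negative self-reports, with CDF: planned in protocol 9.6.1, absent from the SAP text.
- UDS alone in SAP 9.5.1: subjects with a non-negative result for each substance, by subject type; by-visit tables and figures for non-opioid substances; listings.
- TLFB alone in SAP 9.5.1: listings only.
- SAP 9.5.1 also plans a table of the percentage of subjects negative at each visit. It does not name the source. In context it is the combined result. In either case it is a percentage across subjects at a visit, not a percentage of samples within a subject.

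**2. Whether the combined percentage can stand in for the separate ones**

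Let U and T be the shares of visits negative by urine and by self-report, and C the share negative on both. Then max(0, U + T − 1) ≤ C ≤ min(U, T). With assumed values:

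- U = T = 80%: C lies between 80 + 80 − 100 = 60% and 80%.
- U = 90%, T = 70%: C lies between 90 + 70 − 100 = 60% and 70%.

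Read the other way, C = 60% fits U = 100% with T = 60%, and equally U = 60% with T = 100%. The combined figure is only a lower bound for each source.

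**3. What the faulty item can do in the primary analysis**

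Protocol Appendices 2 to 5 schedule UDS at 20 visits after Day 1 for a de novo subject. TLFB is scheduled at the same visits except Day 2, so 19 visits have both. Assume all urines are negative and the only positive TLFB answer is on the amphetamine/methadone item, at 4 visits:

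- primary combined result: (19 − 4)/19 = 15/19 = 78.9%, below the 80% success cut;
- urine alone: 19/19 = 100%;
- planned sensitivity analysis: 19/19 = 100%.

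The 4 visits are an assumption. The documents do not say how often the item was answered positively.

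**4. Day 2**

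Day 2 has a scheduled UDS but no scheduled TLFB. If Day 2 is counted and the absent TLFB is treated as missing, the combined percentage cannot exceed 13/14 = 92.9% for a roll-over subject or 19/20 = 95.0% for a de novo subject. The SAP does not say whether Day 2 is counted. A urine-only summary does not have this ceiling.

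**The case against.** The strongest reply is that the combined endpoint is openly defined in SAP 5.0 with a results table and a missing-data rule, that it is stricter than either source alone, and that the protocol leaves endpoint definition to the SAP. Protocol 9.8 already uses urine combined with self-report in a time-to-event example. This shows that the construct is not new and is not hidden. It does not replace the two CDFs in protocol 9.6.1, and a stricter measure still cannot be separated into its parts.

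Several stronger readings are tempting, and the documents do not support them.

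- *That urine is never reported alone.* SAP 9.5.1 reports UDS by substance. The missing output is narrower: the percentage of opioid-negative samples per subject, and its CDF.
- *That every abstinence result carries the TLFB error.* The primary results do. The sensitivity analysis removes the effect of the one error that the SAP admits, and it returns the subject in step 3 to 100%. What stands is that the SAP does not say which outputs it covers.
- *That counting self-reported buprenorphine as an opioid is a second error.* It is a stated choice. Subjects agree to take no buprenorphine other than study product, and urine was not tested for it at baseline or after RBP-6000, so self-report is the only one of the two sources that could show non-study use.
- *That the change was driven by data.* SAP version 3.0 follows an interim safety analysis, but the documents do not show when the combined endpoint was adopted.

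The study is also open-label, with a safety objective, and no test or decision rests on these curves. That limits the consequence and is accepted.

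**Conclusion.** The point holds in this form: following the SAP text drops two descriptive secondary analyses that the protocol plans, leaves two variables in SAP 4.2 without a matching percent-negative analysis, and does not declare the change. The combined percentage does not make up for the loss, because 80% negative on each source can appear as anything from 60% to 80%. No error rate, sample size or primary conclusion is affected.

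Two limits apply. The percentages in the working rest on assumed inputs and show what is possible, not what happened. The table shells are in a separate document that was not available and may contain UDS-only or TLFB-only outputs; if they do, the SAP text should say so.

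**What to change.** In SAP 9.5.1, add UDS-only and TLFB-only CDFs and percent-negative summaries by subject type, next to the combined endpoint and with the same rule that missing counts as non-negative. State which scheduled visits form each denominator, including whether Day 2 counts.

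In SAP 1.1, list the combined endpoint as an addition to the protocol's analyses. In SAP 9.5.1, state that the amphetamine/methadone sensitivity analysis covers the TLFB-only and combined outputs.

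Declaring the change in SAP 1.1 without adding the outputs would correct the record but would not restore the planned analysis. The cost is two figures with their tables from datasets that already exist, their sensitivity versions where TLFB is involved, and a few lines of text. No new data are needed.

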## 9.7 Other Analyses

### 9.7.1 PK/PD Modeling

The population PK model established using the data collected in the double-blind, placebo-controlled, efficacy study (Study RB-US-13-0001) will be refined using the PK samples collected in the present study to characterize the disposition of buprenorphine and norbuprenorphine following SC injections of RBP-6000, with the assessment of potential covariates affecting the PK of both compounds. Subsequently, the relationships between buprenorphine plasma concentrations and clinical outcomes assessments will be investigated.

These relationships will be initially assessed in a descriptive manner, and, if applicable, appropriate PK/PD models will be developed to describe these relationships. A stand-alone modeling analysis plan will be generated, and the results will be reported in a standalone modeling report.

### 9.7.2 Health Economic and Outcomes Assessment

The health economic and outcomes research endpoints for this study are:

- EQ-5D-5L
- SF-36v2
- MSQ
- HCRU
- TEA
- ASI Lite
- BDI-II
- BPI

Summary scores for these measures will be calculated, as appropriate. Categorical variables will be summarized using frequencies and percentages. Continuous measures will be summarized using descriptive statistics (mean, standard deviation, median, minimum, maximum) as appropriate. An analysis of change will be conducted. A stand-alone statistical analysis plan will be developed prior to database lock for health economics and outcomes research assessments.

A separate stand-alone SAP will be developed prior to database lock with full detail regarding health economics and outcomes analyses.

## 9.8 Handling of Missing Data

For dichotomous outcome measures such as UDS results (negative; non-negative) and self-reports for illicit opioid use (negative; non-negative), any missing observation will be recorded as “non-negative.” For all continuous endpoints (e.g., COWS, SOWS, and VAS), the missing data mechanism will be assumed to be either missing completely at random (MCAR) or missing at random (MAR). The missing data will not be imputed because the analysis method, mixed model for repeated measures (MMRM), does not require any imputation and no sensitivity analyses will be performed on these variables. For time-to-event variables, if the event of interest is not observed prior to withdrawal or end of treatment, the observations will be censored at the time of withdrawal or at the end of treatment. For example, if some subjects still have not had a urine sample negative for opioids combined with self-reports negative for illicit opioid use when the study ends or at the time of withdrawal from the study, then the time to first urine sample negative for opioids combined with self-reports negative for illicit opioid use will be censored at the last time they were assessed.

## **9.9 Subjects Who Withdraw from the Study**

Subjects who withdraw after receiving RBP-6000 will not be replaced.

## **9.10 Interim Analyses**

An Interim analysis will be performed once at least 100 subjects have completed the study.

#### **10.1.2 Investigational Site(s)**

This study will be conducted at up to 50 sites in the US.

#### **10.1.3 Laboratories**

The safety laboratory tests (serum chemistry, hematology, serology, and urinalysis), as well as the specialty laboratory tests (Bioanalytical and Pharmacokinetic) will be conducted at a central laboratory that is certified and accredited to perform the assigned assessments.

Collection of safety laboratory samples is described in Section 6.6.2. The Clinical Laboratory will provide normal ranges and collection, processing, and shipping instructions to the sites in a separate laboratory reference manual.

### **10.2 Institutional Review Board or Independent Ethics Committee Approval**

The protocol will be reviewed by an independent, appropriately constituted, centralized IRB/Independent Ethics Committee (IEC). Study enrolment and protocol related procedures, which do not form part of the subject's normal clinical treatment, will not be performed until the IRB/IEC of record has provided written approval of the protocol or a modification thereof. The IRB/IEC must be constituted and operate in accordance with the principles and requirements of ICH GCP.

Study drug can only be supplied to the Investigator after documentation on all ethical and legal requirements for starting the study has been received by the Sponsor. This documentation must also include an IRB/IEC membership list that contains member's occupations. If the IRB/IEC will not disclose the names of the committee members, the IRB/IEC Federalwide Assurance Number may be accepted as a substitute for this list. Formal approval by the IRB/IEC should mention the study title, study code, study site (or region or area of jurisdiction, as applicable), and any other documents reviewed. It must mention the date on which the decision was made and must be officially signed by a committee member.

